### **C. OPTIONAL ON-STUDY TUMOR BIOPSIES**

Two additional tumor biopsies will be collected for those subjects who provide consent. A biopsy will be collected On-therapy sometime after the completion of 2 cycles of therapy, and/or a biopsy will be collected at 6 weeks post-treatment in patients with disease progression.. Samples will be collected and shipped according to the instructions provided for the Pretreatment Tumor Tissue Biopsy.

[figure not shown]
## II. **BLOOD SAMPLES**

### **A. CYTOKINE Plasma Sample Blood Collection and preparation (includes C-reactive protein analysis at pretreatment and at cycle 2, day 1)**

1. Collect 7cc to 10cc whole blood into EDTA tubes (Purple top). \* At Cycle 1, day 1 predose timepoint only: Make two to three **blood smear slides** and air dry, and save them at room temperature until shipment to the central lab.
2. Process within 2 hours of collection. Cells are removed from plasma by centrifugation for 10 minutes at 1,000-2,000 rpm using a refrigerated centrifuge. Centrifugation for 15 minutes at 2,000 rpm depletes platelets in the plasma sample. The resulting supernatant is designated plasma.
3. Following centrifugation, immediately transfer the plasma apportioned into two clean polypropylene aliquot tubes using a pipette. The samples should be maintained at 2-8°C while handling. Store and at -20°C, or lower until shipment to the central lab. It is important to avoid freeze/thaw cycles. Samples which are hemolyzed, icteric, or lipemic can invalidate certain tests.
4. Transfer the cell pellet to a 50 ml Falcon tube which contains 40 ml ice cold ddH2O. Mix it gently by inverting tube for several times to lyse the red cells (about 10 sec). Then divide the mixture into two 50mL Falcon tubes in equal volume, add 25 ml 2 X PBS in each tube and mix it gently by inverting the tube several times. Centrifuge the tubes at 1000 rpm (250g) for 10 min, remove supernatant and re-suspended the cell pellets in 500µL 1XPBS of each. Transfer both into a clean polypropylene aliquot tube, centrifuge at 2000g for 5 min. Discard the supernatant, and save the cell pellet in -80°C until shipment to the central lab. Label it with **whole cell pellet**.
5. Send blood smear, plasma sample and whole cell pellet to the central lab according to the shipment instruction below. **B. CYTOKINE Peripheral Blood Mononuclear Cell (PBMC) Sample Collection and preparation**
  1. Collect 10cc whole blood into EDTA tubes (**purple** top). Process within 2 hours of collection according to Ficoll-Hypaque method:
  2. Place fresh heparinized blood into 15- or 50-ml conical centrifuge tubes. Using a sterile pipet, add an equal volume of room-temperature 1 × PBS. Mix well.

- Pellet the leukocyte/RBC fraction by centrifuging the cells 15 min at  $200 \times g$ , room temperature. The platelet cell fraction will remain in the upper suspension. Using a sterile pipet, remove the supernatant suspension containing this platelet cell fraction. The blood should immediately be gently mixed, and should be examined when it reaches the laboratory for small blood clots. As the clotting reaction releases proteins that can affect lymphocyte phenotype and function, samples containing clots should be discarded.
- Using a sterile pipet, add an equal volume of room-temperature  $1 \times$  PBS suspension (if utilizing a 15-ml conical tube) or bring the leukocyte/RBC cell suspension to a final volume of 40 ml with  $1 \times$  PBS (if utilizing a 50-ml conical tube).
- Slowly layer the Ficoll-Hypaque solution underneath the leukocyte/RBC/PBS mixture by placing the tip of the pipet containing the Ficoll-Hypaque at the bottom of the sample tube. Use 3ml Ficoll-Hypaque per 10ml blood/PBS mixture. Use a maximum of 10 ml Ficoll-Hypaque per 40 ml leukocyte/RBC/PBS mixture.

To maintain the Ficoll-Hypaque/blood interface, it is helpful to hold the centrifuge tube at a  $45^\circ$  angle. Alternatively, the leukocyte/RBC/PBS mixture may be slowly layered over the Ficoll-Hypaque solution. *See Figure below.*

**Figure 7.1.1** Ficoll-Hypaque density isolation of mononuclear cells. Ficoll-Hypaque is underlayered onto whole blood or cord blood. The sample is centrifuged allowing the separation of lymphocyte cell population from other blood elements based upon density gradient.

- Centrifuge 20 to 30 min at 2000 rpm ( $900 \times g$ ),  $18^\circ$  to  $20^\circ\text{C}$ , with no brake.

After a centrifugation with Ficoll-Hypaque, platelets (specific gravity, 1.040) and plasma (specific gravity, 1.025 to 1.029) are located above the Ficoll-Hypaque, lymphocytes (specific gravity, 1.070), and some platelets are found at the plasma-

Ficoll-Hypaque interface. Granulocytes (specific gravity, 1.087 to 1.092) and RBCs (specific gravity, 1.093 to 1.096) form a cell pellet at the bottom of the tube (see Fig. below)

[figure not shown]

Figure 7.1.2 Separation of blood components on a Ficoll-Hypaque gradient.

7. Using a sterile pipet, remove the upper layer that contains the plasma and most of the remaining cell platelet fraction. Using another pipet, transfer the mononuclear lymphocyte cell layer to another centrifuge tube. This will appear as a white, cloudy band between the plasma and the Ficoll-Hypaque layers. Wash cells by adding HBSS (~3 times the volume of the mononuclear cell layer) and centrifuging 10 min at 450 to 600 $\times$ g, 18° to 20°C. Remove supernatant, re-suspend cells in HBSS, and repeat the wash once to remove any remaining platelets.

The washing steps described above usually remove most of the platelets from the mononuclear cell suspension. There are certain disease states associated with increased platelet concentrations (mononuclear cell to platelet cell ratio  $>10:1$ ) in the peripheral blood, and additional steps are needed to remove the extra platelets in these cases. Add 3 ml FBS to a centrifuge tube for each milliliter of mononuclear cells. Layer the cell suspension ( $1-2 \times 10^7$  cells/ml) over the FBS (alternatively, carefully layer the FBS under the cell suspension, which will rise as FBS is added). Centrifuge 15 min at 150  $\times$  g, 18° to 20°C. Discard the supernatant containing the platelets. Re-suspend cell pellet in complete RPMI-1640 and proceed as in step 8.

8. Re-suspend mononuclear lymphocyte cells in complete RPMI-1640. Count cells and determine viability by trypan blue exclusion. If desired, purity of PBMC population can be determined by flow cytometry.

9. Centrifuge 5 min at 2000  $\times$  g, 18° to 20°C. Discard the supernatant and save the PBMC in -80°C until shipment to the central lab. Label it clearly with "PBMC" and estimate cell number.

10. Freeze sample in one aliquot tube at -80C until shipment to the central lab. See shipping instructions.

Shipment of Cytokine Plasma and PBMC samples (includes C-reactive protein at Pre-treatment and at Cycle 2, day 1):

1. Samples may be batched and shipped on a monthly basis.
2. Package samples according to IATA regulations.
2. Label specimens appropriately with subject study ID, date and time of collection, and type of collection (plasma or PBMC). Complete and fax the completed Blood Sample Requisition and Shipment Notification Form on the day of shipment and include a copy of the form in the shipment.
3. Slides made from the C1, D1 predose timepoint will be transported at ambient temperature using overnight express service.

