diarrhea (10 subjects) and fatigue (8 subjects). Both anemia and thrombocytopenia represent JAK-inhibitor induced myelosuppression. Forty (40) subjects (26% of study population) had a Grade 3 or Grade 4 decline in platelet count during the study (31 Grade 3 events, 9 Grade 4 events). Subjects with Grade 3 or 4 thrombocytopenia entered the study, in general, with platelet counts less than 200 K/ $\mu$ L, although there are exceptions to this trend. Twenty percent of Grade 3 + 4 thrombocytopenia events occurred in the first 4 weeks of dosing, just under half (48%) of Grade 3 + 4 events occurred in the first 16 weeks of treatment. The incidence of thrombocytopenia was dose dependent, as anticipated. For most subjects, thrombocytopenia was rapidly reversible and manageable with ruxolitinib dose interruption and/or dose reduction. Anemia, in general, reflected the low hemoglobin status at baseline in this disease population.

Ruxolitinib has demonstrated marked reduction in spleen size in the ongoing study in patients with MF, and without regard to presence of the JAK2 V617F mutation. In addition to spleen size reduction, Eastern Cooperative Oncology Group (ECOG) scores and symptoms thought to be related to splenomegaly, as well as symptoms related to elevated cytokine levels, all show improvement with ruxolitinib treatment. As a surrogate marker for functional benefit, exercise capacity was assessed with a standardized six minute walk test (6MWT). ruxolitinib therapy resulted in improved 6MWT performance after 1, 3 or 6 months of therapy. After an initial small weight loss likely due to resolution of ascites and/or reduction in splenomegaly, there is an increase in total body weight; importantly, there is weight gain in subjects with low body mass index at entry, i.e., cachectic subjects. See the Investigator's Brochure for additional details.

In Study INCB 18424-256 in patients with advanced PV or ET, and after a median follow-up of 15 months (range 8-21), 97% of enrolled PV subjects achieved Hct control to < 45% in the absence of phlebotomy, and all continued to maintain phlebotomy-independence at the time of last follow-up visit. Prior to treatment with ruxolitinib, twenty-six subjects were phlebotomy-dependent with the majority being maintained on

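### Appendix 2 allows a cytokine plasma spin that, by its own figures, may leave platelets in the plasma, and does not say whether the platelet-depleting spin is required

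*Combined protocol and SAP*

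**What the plan says.** Section 5.2.2 collects serial blood for cytokines and chemokines, measured in plasma and mononuclear cells: before the first dose, 3 hours after it, on Days 8, 15 and 22, and on Cycle 2 Day 1. Appendix 2 gives the processing.

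- **II.A step 2, first sentence:** "Cells are removed from plasma by centrifugation for 10 minutes at 1,000-2,000 rpm using a refrigerated centrifuge".
- **II.A step 2, second sentence:** "Centrifugation for 15 minutes at 2,000 rpm depletes platelets in the plasma sample".
- **II.A step 2, third sentence:** "The resulting supernatant is designated plasma". It does not say which of the two spins produces that supernatant.
- **II.A step 3:** the plasma is aliquoted and frozen, with no further spin or filtration: "Store and at -20°C, or lower until shipment to the central lab".
- **II.A step 4**, on the cell pellet, gives a speed conversion: "Centrifuge the tubes at 1000 rpm (250g) for 10 min".
- **II.B**, on mononuclear cells, starts with a 15-minute spin at 200 g of blood diluted with an equal volume of PBS, and says of it: "The platelet cell fraction will remain in the upper suspension". Later it sets 2,000 rpm equal to 900 g.

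On the drug, the Clinical Summary in section 3.1 says of the myelofibrosis study: "The incidence of thrombocytopenia was dose dependent, as anticipated". Section 12.2.3 plans a paired t-test of marker change from before to after treatment, with no mention of platelet count.

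**The concern.** A site that spins every plasma tube at 1,000 rpm for 10 minutes complies with step 2 as written. If that leaves platelets behind, they are frozen with the plasma. How many remain would depend on the speed the site chose and on the subject's platelet count that day. Speed varies at the site's discretion, and the count can fall on treatment.

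If residual platelets add to the measured chemokines, a falling count would lower that part of the signal, and the fall would look like a pharmacodynamic effect of the drug. What is at stake is the interpretation of the serial plasma cytokine and chemokine results, which are exploratory. Platelets frozen into a sample cannot be dependably removed later, so the protection has to come at processing.

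**Working it through.** The plan states no figure for residual platelets, so there is none to reproduce. The check compares the spins by force x time (g x minutes). This is a simple proxy for sedimentation and not a platelet count.

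**Conversions.** At a fixed rotor radius, g rises with the square of rpm.
- II.A step 4: 1,000 rpm = 250 g. Scaled to 2,000 rpm: 250 x (2,000/1,000)² = 1,000 g.
- II.B: "Centrifuge 20 to 30 min at 2000 rpm", given there as 900 g. The two pairs do not quite agree, so 2,000 rpm is taken as 900-1,000 g.

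**Comparison.**

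| Spin | Source | g x min |
|---|---|---|
| Weakest permitted plasma spin | II.A step 2 (g from step 4) | 250 x 10 = 2,500 |
| Said to leave platelets in the supernatant | II.B | 200 x 15 = 3,000 |
| Strongest spin in the 10-minute range | II.A step 2 | 900-1,000 x 10 = 9,000-10,000 |
| Said to deplete platelets | II.A step 2 | 900-1,000 x 15 = 13,500-15,000 |

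- Weakest permitted against platelet-retaining: 2,500 / 3,000 = 83%.
- Weakest permitted against platelet-depleting: 2,500 / 15,000 = 17%, or 2,500 / 13,500 = 19%. On any single rotor the ratio is (1,000/2,000)² x 10/15 = 1/6.
- Strongest 10-minute spin against platelet-depleting: 10/15 = 67%. It is at least three times the platelet-retaining spin, so the appendix does not show that platelets remain there. The finding is firm only for the lower end of the range.

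**Rotor.** Step 2 gives rpm without a radius. With g = 1.118 x 10⁻⁵ x r(cm) x rpm², the two conversions imply radii of 22.4 cm and 20.1 cm. On an assumed 10-15 cm rotor, 1,000 rpm gives only 112-168 g. The range itself spans a fourfold difference in g on one rotor.

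**Platelet falls in the sampling window.** The only source is the myelofibrosis study in section 3.1 (N = 154).
- Forty subjects (26%) had a Grade 3 or 4 decline, and 20% of these events came in the first 4 weeks: 0.20 x 40 = 8, and 8/154 = 5%, taking one event per subject. In a cohort of 30 that is 30 x 8/154 = 1.6 subjects.
- Related thrombocytopenia was reported in 66/154 = 43%, but over a median of about 15 months on drug.
- In this trial, sampling ends at Cycle 2 Day 1, and section 9.2.2 permits dose increases only after 2 cycles, so no planned increase falls inside the window.

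The documents give no figure for smaller early falls, which would also enter a mean change.

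**The case against.** **The 15-minute spin may already be meant as a second step.** Neither sentence in step 2 is an instruction. The second speaks of the plasma sample, as if cells had already been removed, and the sentence defining plasma follows directly. Read in sequence, the platelets are removed and there is no defect. This reading is fair, but nothing requires it. Two reasonable readings lead to very different platelet content, so the step needs settling.

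**The link to the readout is outside the documents.** They do not say that platelets release chemokines, and they list no analytes. This stands: the link is an assumption.

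**The analysis link is inferred.** Section 12.2.3 names expression signatures, immunophenotypic pathway markers and tumor samples, not plasma cytokines, and cytokine profiling is absent from the objectives in section 4.3. This stands too: the paired t-test is the only marker-change analysis described, but it is not tied to these samples.

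**A speed held constant at a site does not itself bias within-subject change.** Correct. However, a constantly weak spin still lets a falling platelet count through, and nothing requires the speed to be constant or recorded.

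**A stronger reading that does not hold.** A reader might infer that the chemokine results would track thrombocytopenia instead of cytokine signalling, and might size this by multiplying an assumed platelet-derived share by an assumed platelet fall. Shares of 30-90% and falls of 20-50% give 0.3 x 0.2 = 6% to 0.9 x 0.5 = 45%. Neither factor comes from the documents, so that range reflects only the guesses. The 43% from the myelofibrosis study does not supply it either, because it covers a much longer exposure.

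**Conclusion.** Step 2 permits a plasma spin weaker than one the same appendix says leaves platelets in the supernatant, and about one-sixth of the one it says depletes them. It does not say whether the depleting spin is mandatory. That much rests on the appendix's own text and conversions, with force x time as an approximate yardstick; the II.B comparison uses diluted blood.

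The consequence is conditional. If platelets release chemokines on freezing, on-treatment changes in plasma chemokines could be partly confounded by a falling platelet count. The documents support neither a size for this nor a claim that it replaces the signalling effect. About 5% of subjects would be expected to have a Grade 3 or 4 decline within 4 weeks on the myelofibrosis figures, and the 3-hour sample is unlikely to be affected. The reach is limited to an exploratory evaluation; the overall response rate analysis and its error rates are untouched. The change is worth making because it is cheap and the problem is hard to undo once samples are frozen.

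**What to change.** In Appendix 2 II.A step 2:

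1. Delete the 10-minute, 1,000-2,000 rpm range.
2. Make the spin the text already calls platelet-depleting (15 minutes at 2,000 rpm) a required step for every plasma sample.
3. Restate it as one x g value. The appendix's own pairs give 900 g and 1,000 g for 2,000 rpm, so the central laboratory should settle which applies.
4. Record the spin used for each sample.

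Apply the change from a subject's first sample onward, because switching spins partway through a series would itself produce a before-after difference.

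For samples already collected, report the spin used and show chemokine change alongside the same-day platelet count. The schedule in section 7.1 already draws hematology on Days 8, 15 and 22 and Cycle 2 Day 1, with a baseline value allowed within 7 days before dosing. Present this as a descriptive sensitivity check only: the drug itself affects platelet count, so adjusting for it could remove part of a genuine effect.

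Cost: about 5 more minutes of centrifuge time per sample (15 - 10), one revised line in the appendix and one recorded item. No additional blood is needed.

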### **Plasma**

Collect 7cc to 10cc blood in a light green-top (lithium heparin) gel tube(s). Spin down and send 1 mL of lithium heparin plasma. Store at -80.

**Note:** Indicate plasma on request form.

## **APPENDIX 3 – GRADING OF ADVERSE EVENTS**

Adverse Events will be graded according to the National Cancer Institute Common Toxicity Criteria for Adverse Events (CTCAE), Version 4, which may be found at the following website:

[http://ctep.cancer.gov/protocolDevelopment/electronic\\_applications/ctc.htm#ctc\\_40](http://ctep.cancer.gov/protocolDevelopment/electronic_applications/ctc.htm#ctc_40)
